1.7 Vitamin D status, GDM and Pregnancy

Vitamin D insufficiency has now reached epidemic proportions, even in healthy individuals living in the tropics ¹⁷⁶. Use of HAART has been a possible cause of hypovitaminosis D ¹⁷⁶. Recent evidence links not only low maternal vitamin D status with increased risk of severe preeclampsia or small-forgestational age but also schizophrenia in the offspring. Other Foetal risks include intrauterine growth retardation, neonatal hypocalcemic seizures, impaired postnatal growth, rickets in infancy and cardiomyopathy with increased future risks of asthma and type 1 diabetes. Polymorphisms in the vitamin D receptor (VDR) gene may contribute to vitamin D-related disparities in feotal growth. Evidence from recent studies suggests an early prenatal influence of maternal vitamin D status on feotal skeletal development.¹⁷⁷. Vitamin D status has also been shown to have a significant inverse association with TB incidence ^{178;179}. Vitamin D exerts its action through VDR and the gene polymorphisms associated with susceptibility or resistance to TB¹⁸⁰. Vitamin D, selenium and zinc play fundamental roles in determining susceptibility to infections including accelerated HIV disease progression ^{181;182}. Currently little is known regarding the effects of HIV/AIDS and its treatment on the metabolism of vitamin D and pregnant income and susceptibility to infections. Being a potent immunomodulator, vitamin D's impact on morbidity and mortality among infants remains poorly described. There is a particular need for maternal education on healthy diet and for interventions which aim to limit over consumption of excess calories or insufficient nutrition during feotal vulnerable developmental periods appears to result in a lifelong predisposition to obesity and adult disease, such as cardiac diseases and type 2 diabetes. Maternal vitamin D levels exhibit a significant negative relationship with glycosylated haemoglobin (HbA1c) levels, supporting a potential role for this vitamin in maintaining glycaemic control ¹⁸³. Pregnancy is also a risk factor for impaired glucose metabolism. GDM is defined as glucose intolerance of variable degree with onset or first recognition during pregnancy. Carrying a male fetus has been associated with poorer maternal beta cell function and an increased risk of GDM ¹⁸⁴. Studies have given conflicting results regarding the contribution of PIs to impaired glucose tolerance and GDM in pregnant HIV-infected women. Betatrophin, also known as TD26/RIFL/lipasin/ANGPTL8/C19/f80, is a novel protein predominantly expressed in human liver. Betatrophin plays a significant role in the regulation of lipid metabolism and glucose homeostasis, positively correlating with weight gain during pregnancy, systolic blood pressure, very low-density lipoprotein levels, fasting insulin level and homeostatic model assessment insulin resistance 185;186.

GDM is associated with many adverse neonatal and maternal outcomes miscarriage, infants being large for gestational age (LGA) requiring a Caesarean delivery. A growing body of literature supports

a relationship between intrauterine exposure to maternal diabetes and risk of a metabolic syndrome childhood obesity, hypertension, dyslipidaemia, and glucose intolerance later in life. Glycosylated haemoglobin values (HbA1C) levels are associated with increased risk for malformation. HbA1C is a reliable measure of chronic glycemic control without the need for a fasting or timed sample. Infants born to mothers with diabetes have been shown to exhibit higher levels of cardiovascular risk biomarkers for endothelial damage and inflammation, higher leptin levels, BMI, waist circumference and systolic blood pressure but decreased adiponectin levels. Maternal GDM, low socioeconomic status and preterm infants have been associated with an increased risk of neurocognitive development especially the attention-deficit/hyperactivity disorder (ADHD) and compromised neurobehavioral functioning ¹⁸⁷. GDM birth anomalies also involve cardiovascular diseases (CVD). CVD complicates pregnancies with congenital heart disease being the most common pre-existing condition and hypertension as the most common acquired condition.

1.8 Hypertensive Disorders

Hypertensive disorders during pregnancy represent the major cause of maternal morbidity with chronic hypertension occurring in up to 5% of pregnant womenworldwide¹⁸⁸. Mild to moderate hypertension in pregnancy is defined as systolic blood pressure of 140-159 mmHg or diastolic blood pressure of 90-109 mmHg. Hypertension during pregnancy is classified into three main categories: chronic hypertension, gestational hypertension, and preeclampsia (high blood pressure and proteinuria) with or without pre-existing hypertension. The occurrence of postpartum depression and anxiety is higher in pre-eclamptic women ¹⁸⁸. Chronic hypertension is defined as blood pressure >140/90 mm Hg that either precedes pregnancy or develops before 20 weeks gestation usually also persists beyond 42 days postpartum. Chronic hypertension is significantly higher among obese women ¹⁸⁹.Hypertension during pregnancy is more likely in women with high baseline systolic blood pressure and those with higher MUAC 190. Diet has been suggested to play a role in preeclampsia.Maternal serum concentration of the soluble receptor-1 of tumor necrosis factor-alpha (TNF-R1) a predictor of development of pre-eclampsia. Oxidative stress and endothelial cell dysfunction of the placenta have been implicated in the development of hypertension during pregnancy and vitamin intake can reduce oxidative stress and improve endothelial function ^{191;192}.Endothelial dysfunction biomarkers include VonWillebrand factor (vWF), platelet derived micro particles (PMPs), and endothelin-1 that are easily analysed by ELISA. Other serum/plasma biomarkers associated with increased risk of hypertensive disorders of pregnancy that correlate with adverse pregnancy outcomes include soluble corin, vascular endothelial growth factor, matrix metalloproteinase-1 and tissue inhibitor of metalloproteinase-1 (TIMP-1). Haemolysis, elevated liver enzymes and low platelet count (HELLP) syndrome is a risk factor for preeclampsia. HELLP is a lifethreatening obstetric complication usually beginning during the third trimester. It is characterized by

15

low platelet count, less than 100000. Serum aspartate aminotransferase (AST) and lactic dehydrogenase lactic dehydrogenase levels of greater than 70 U/L, and 600 U/L, respectively. HELLP syndrome not only increases maternal morbidity and mortality but also that of the fetus. Thrombocytopenia is defined as a platelet count of less than $150 \times 10^3 \mu$ l. It is commonly diagnosed and has attracted interest from the researchers in pregnant women especially among hypertensive pregnant women. Gestational thrombocytopenia defined as a platelet count of less than $150 \times 10^{3} \mu l$ is recognized as a major cause of thrombocytopenia particularly in hypertensive pregnant women during the third trimester. Hypertension during pregnancy increases feotal growth retardation, preterm deliveries, still births and perinatal deaths, yet its causes remain unclear ¹⁹⁰. Hypertension and pregnancy outcomes remain poorly described in our setting more so comparing and contrasting between HIV positive and negative pregnant women. HIV-infected women using HAART before conception have been shown to be at increased risk of developing preeclampsia/eclampsia during pregnancy among Latin American women¹⁹³. Contradicting evidence exists concerning the relationship between HIV infection, HAART use and hypertensive disorders in pregnancy. In addition there are indications of hypertensive disorders of pregnancy being associated with high infant blood pressure. Moreover, the trends blood pressure changes across childhood remain poorly described.A history of pre-eclampsia or pregnancy induced hypertension is an important prognostic factor for micro- and macro-vascular complications later in life. CVD factors such as obesity, diabetes, and hypertension hyperlipidemia, and thrombophilia which are associated with increased risk of spontaneous abortion, preterm labour or premature rupture of membranes, and acute arterial or venous thromboses during pregnancy. Of course just like in any condition, host genetic factors also play a significant role.

1.9 **Host genetics**

A myriad of host and viral factors act in tandem to cause vertical transmission of HIV. Understanding the mechanisms, host and viral factors associated with vertical transmission of HIV will help to identify appropriate interventions and suitable antiretroviral chemoprophylaxis regimens to reduce or eliminate it. Increasing data support host genetic factors as important determinants of HIV-1 susceptibility, vertical transmission and disease progression with the CC chemokine CCL3 and HLA taking the centre stage ¹⁹⁴⁻¹⁹⁸. Relative resistance to HIV infection has been associated with genetic polymorphisms. The killer cell immunoglobulin-like receptors (KIR) play a fundamental role in the innate immune system. KIR genes are incredibly polymorphic both in the number of genes an individual carries and in the number of alleles identified ¹⁹⁹. However, their interactions with HLA molecules, leading to the modulation of activity in NK cells, mainly related to killing pathogeninfected cells remain poorly described. Typing of HLA loci B, Cw, and killer cell KIR molecules has shown that the reciprocal equilibrium between inhibitory and activatory NK receptors and their ligands favour NK activation among HEU adults ¹⁹⁹. A trend toward increased early HIV-1 acquisition among Kenyan infants presenting in HLA A*29 and increased late HIV-1 acquisition via breast milk for both Cw*07 and Cw*08. HLA B*18 may protect breast-feeding infants against both early and late HIV-1 acquisition, a finding that could have implications for the design and monitoring of HIV-1 vaccines targeting cellular immune responses against HIV-1²⁰⁰. Placental HLA-G1 expression has been shown to be up-regulated 4 times more in placentas of HIV-1 infected mothers with infected babies compared to uninfected babies ²⁰¹. Single nucleotide polymorphisms and copy number variations have been documented for defensins chemokines and RFs which are natural inhibitors of HIV infection ²⁰²⁻²⁰⁵. These results demonstrate a significant relationship between genetic variants of beta-defensin-1 gene, RFs genes, viral load, and vertical transmission of HIV-1, thus supporting a critical role of innate immunity in paediatric HIV-1 infection. However, such studies are rare in the region.

1.10 HIV Genetic Diversity

HIV-1 genetic diversity in the HEI may also affect viral transmissibility, pathogenicity and responses to antiretroviral therapy. Variable region 3 (V3) of the envelope (env) gene for CCR5 and CXCR4 determination is a key determinant of vertical transmission ^{206;207}. HIV-1 env gp (glycoprotein)120 variable regions exhibit an unusual pattern with encoded amino acids (asparagine, serine and threenine) that leads to the creation of new N-linked glycosylation sites, which helps the virus to escape from the immune pressure ^{208;209}. Potential N glycosylation sites (PNGs) glycans and amino acid length polymorphism have been shown to play essential roles in disease progression with changes potentially affecting the capacity of the virus to replicate ^{210;211}. Studies have shown that at birth all HIV infected infants' env amino acid sequences are initially of the same length as the maternal ones with amino acid sequence length polymorphism observed from six months postpartum ²¹². However, other studies have observed no clear trends in changes in neither the env PNGs nor median amino acid lengths with disease progression ²¹³. Genetic analyses revealed that rapid paediatric progressors receive and maintain a genetically homogeneous viral population throughout the disease course whilst slow progressors' exhibit low levels of variation ²¹² initially, but attain higher levels of diversity over time a phenomenon important in HIV transmission linkages. Phylogenetic and phylodynamic studies have identified clusters of new infections occurring along geographic routes and in different groups²¹⁴⁻²¹⁶. Late diagnosis of HIV remains prevalent and represents missed opportunities for early treatment. The combination of phylogenetic analyses of HIV sequences with patients' demographic data allows greater understanding of local HIV transmission and necessary knowledge for designing prevention strategies. ²¹⁷. The host immune response to HIV in early life is complex. Understanding the relationships between acquired immune responses to HIV, innate immune responses that include chemokines and their receptors, and host genetic influences that affect these immune processes in HIV-exposed infants will help identify critical components of protective immunity. This helps in the identification of infants at risk of acquiring HIV-1 infection and/or at risk of more rapid disease progression. Results from such studies will vastly improve our knowledge of HIV-host interactions. Further elucidation of these processes will contribute to the rational design of vaccines and the development of novel preventative and therapeutic anti-HIV strategies for children exposed to HIV. Having discussed all the foregoing factors shortcomings associated with maternal psycho-social issues and being born in an HIV affected household may also play a pivotal role.

1.11 Maternal Psycho-Social Factors

Undiagnosed maternal HIV infection prior to conception, unplanned pregnancies, delays in accessing antenatal care, non-disclosure of the pregnant women's HIV status to her partner and low levels of education are some of the most significant maternal risk factors associated with vertical transmission and or infant death ²¹⁸⁻²²⁰. Directly disclosing a positive HIV sero-status to family members can have psychological and physiological health benefits ²²¹. Hence disclosure of HIV sero-status by women to their sexual partners is critical for the success of the PMTCT programme as an integrated service in antenatal care. Pregnant HIV-negative women and their unborn babies remained at risk of HIV infection owing to the resistance of their partners to go for HIV testing ²²². Poverty, lack of support, HIV, witchcraft and child illness have been identified as causes of worry in the perinatal period ^{223;224}. Adverse maternal health and feotal outcomes have been shown to be more prevalent in socioeconomically-disadvantaged women²²⁵. Depression and its impact on maternal and child health has important implications with depressed mood being associated with alcohol use, less breastfeeding and low birth weight ^{226;227}. Smoking increases the risk of morbidity and mortality and is particularly harmful to pregnant mothers. Chronic maternal marijuana use has been associated with early sex in offspring ²²⁸.Studies have shown that alcohol use and HIV sero-status of partner predict high-risk sexual behaviour among patients receiving antiretroviral therapy ^{229;230}. Alcohol-exposed pregnancy is a significant public health problem as alcohol consumption is associated with feotal abnormalities and long-term cognitive problems depending on the amount consumed, drinking pattern, and time of gestation. Feotal alcohol exposure is a leading cause of developmental disabilities and mental retardation ²³¹. Prenatal cocaine exposure has been linked to child behaviour problems²²⁸. Screening for alcohol use disorders and substance uses are important to reduce alcohol consumption during pregnancy and associated problems in infants. Intimate partner violence defined as actual or threatened physical, sexual, psychological and emotional abuse by current or former partners is a global public health concern ^{232;233}. Hence there is need to manage health related stress. There is significant current interest in the degree to which prenatal exposures to stress influence infant outcomes. Such maternal psycho-socio and demographic factors also play a role in infant mortality and necessary interventions for common perinatal mental disorders may be required.

There is paucity of information regarding the impact of environmental factors related to being born in an HIV-affected household especially of low social economic status and how this impacts on child care practices. Limited data exists which explores the possible associations between the mothers' psychosocial and economic wellbeing during the prenatal and postnatal period and increased

psychosocial and economic wellbeing during the prenatal and postnatal period and increased morbidity and mortality among HEU infants in the first year of life. It is against this background that in addition to investigating the abnormal immunity of HEU and the associated maternal genetic and environmental factors. For the holistic and integrative research, numerous other related sub-studies addressing other coinfections, NCD and maternal psycho social aspects will be developed for a full assessment of the common comorbidities. Each of these comorbidities in isolation and/or combination may be assigned characteristic immune biomarkers assayed from one blood plasma sample and such a development may lead to powerful tool to optimize and individualize treatment and care. Other sub studies linked to this study also seeking to determine the maternal psychological wellbeing such as stress and depression including other important co-infections such as Tb, herpes simplex virus (HSV), human papilloma virus (HPV), bacterial vaginosis, (BV) infections gut and vaginal microbiomes associated with high morbidity and mortality among HEU infants will be developed. In general, research questions will fall into seven thematic areas namely, co-infections, non-communicable diseases, nutrition, immunogenetics, pharmacokinetics/dynamics/genomics, psychosocial and child growth and development. See **Appendix 6.1**.

1.12 Justification

Viral, host immunogenetics and environmental factors associated with HIV non-acquisition and/or slow HIV disease progression among paediatric patients remain poorly described. The little that is currently known comes from HIV-1 subtype B studies. The role of innate immunity in protection against HIV infection and disease progression may not be over-emphasised among paediatric HIV infected individuals whose adaptive immunity may not have fully developed. Since HIV-infected children progress more rapidly than adults and have fewer background cofactors such as drug use and co-infections and the effects of host genetic factors on HIV-1 disease may be more clearly identified. Most current researches are done in "silos" (focused on single, isolated aspects of immune defense) downplaying systemic and interconnected nature of the arms of the immune system. Yet in real life situation disease acquisition, progression and even response to therapy are multi factorial with environmental and immunogenetic factors playing critical roles. There is need for a cohort to clearly discern the causes or/ and consequences of viral immune profiles which is impossible to determine with cross sectional studies. HEU and non-progressing HEI children offer hope that natural and effective HIV control is possible and can provide important insight to the development of the next generation of HIV/AIDS vaccines and immune-based therapies. There is need for a comprehensive,

integrative and a holistic approach to predict diseases outcomes.HIV infection and co-infections, immune profiles, nutritional status that may influence transmission, disease progression and immune development and these will be assessed from baseline.

2.0 Research Questions

- 1. Is the increased morbidity and mortality of HEU infants associated with increased exposure to maternal HIV load, other maternal co-infections (HBV, HCV, CMV, intestinal parasites) and how do these affect pregnant outcome and child growth and development?
- 2. Is the incidence of comorbidities, anaemia, diabetes, malnutrition and hypertensive disorders similar between HIV positive and HIV negative pregnant women and how do these affect pregnant outcome and child growth and development?
- 3. Is there a difference in biomarkers of inflammation and immune activation among mothers (HIV+/HIV-) and their (HUU/HEU/HEI) infants with different comorbidities?

2.1 Main Hypotheses

- There is no difference in the prevalence and incidence of co-morbidities (anaemia, malnutrition, hypertension, diabetes, HCV, HBV, CMV) and immune profile of HIV+ and HIV- pregnant women and the impact of these comorbidities on pregnancy outcome and infant growth and development within 24 months post-delivery is similar.
- 2. There is no difference in biomarkers of inflammation and immune activation profiles among HIV+ and HIV- mothers with different comorbidities and their HEI, HUU HEU infants.

3.0 Project Goals:

- 1. The main goal of this study is to characterise co-morbidities, immunogenetics of pregnant women and their infants in Harare and ascertain their roles in disease acquisition and transmission
- 2. Contribute to the knowledge base on the role of HIV and human immunogenetics on acquisition and disease progression and co-infections in children.

3.1 Main Objective

This study aims to establish a birth cohort to investigate the role of HIV and comorbidities on vertical HIV transmission, immune development and disease progression in children 0-2 years, HEU, HEI and HUU as the control group.

Objectives

A. All Mothers Regardless of HIV Status

- To determine the prevalence and incidence of coinfections (intestinal parasitic infections, HBV, HCV, CMV) malnutrition and non-communicable diseases (NCDs) (gestational diabetes mellitus, hypertensive disorders and CVD) risk factors over 24 months and relate all these comorbidities to:
 - a. Pregnancy outcome, infant growth, development, morbidity and mortality
 - b. Biomarkers of inflammation and immune activations

Infants

- 2. To determine vertically transmitted infections and incidence non-communicable diseases among infants.
- 3. To determine clinical and immunological profiles of HEI, HEU and HUU infants.

B. HIV+ Mothers: Chronic HIV infections

- 1. To determine vertical transmission rates of mothers with acute and chronic HIV infection on option B+
- 2. Determine any association(s) between different option B+ drug regimens, adverse pregnancy outcome, viral load suppression and CD4/CD8 counts on mothers and their infants

C. HIV+ Mothers; Acute HIV infections,

- 1. To determine the incidence of HIV in the postpartum period over the 2 years
- 2. To determine the viral set points, HIV suppression trends and biomarkers of immune activation
- 3. To determine the HIV and host genetic diversity and possible transmission linkages

Infants

To characterise natural killer cell phenotype and function longitudinally from cord blood at birth up to 2 years and relate to infant HIV acquisition , morbidity and mortality

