4.8 Mothers' Procedures

• A questionnaire will be administered at enrolment from which information regarding their sociodemographics, sexual behaviour and reproductive health issues including obstetrical records will be obtained. Antiretroviral use and regimen will be recorded for all the HIV+ mothers. Assessment of nutritional status/BMI will be done using standard anthropometric indices. A physical examination will be done at every visit by the study clinician. Mothers will be enrolled at 28-36 weeks gestation and followed up at delivery, 10 days and 6, 10, 14, 24, 36, 48, 72 and 96 weeks postpartum thus totaling 11 visits during the study period. Data can still be collected in cases of missed visits provided the participant turns up within the seven day window period of the scheduled visits. The participant may be asked to discontinue if she consecutively fails to turn up for at least two successive scheduled study visits without any reason(s).

Biological specimens blood, cord blood, amniotic fluid, breast milk urine and stool will be collected at different visit with the respective quantities and purposes as shown in the **Table** 1 below.

	Total Volume of Specimen Required						
Visit	HIV Status	Blood* (mL)	Stool** (grams)	Breast Milk* (mL)	Urine *** (mL)	Amniotic Fluid (mL)	Cord Blood (mL)
1	HIV+	30	20	-	100	50	
In Pregnancy	HIV-	25	20		100	50	
2 Delivery	HIV+	10	20		100	50	50
	HIV-	5	20		100	50	50
3 7 -10 days pp	HIV+	-	If delivery visit is	10	100		
	HIV-	-	missed some of the samples are collected.	10	100		
4 6 Weeks/1½Months pp	HIV+	20	20	10	100		
	HIV-	10	20	10	100	50	
5 10 Weeks /2½ Months	HIV+	20	20	10	100		
рр	HIV-	10	20	10	100		
6 14 Weeks, 3½Months	HIV+	20	20	10	100		
рр	HIV-	10	20	10	100		
7 24 Weeks/6 Months pp	HIV+	20	20	10	100		
	HIV-	10	20	10	100		
8 36 Weeks/9 Months pp	HIV+	20	20	10	100		
	HIV-	10	20	10	100		
9 48 Weeks/1 year	HIV+	20	20	10	100		
pp	HIV-	10	20	10	100		
10 72 Weeks /1 ^{1/2} years	HIV+	20	20	10	100		
	HIV-	10	20	10	100		
11 96 Weeks/2 years	HIV+	20	20	10	100		
	HIV-	10	20	10	100		

Table 1: Types and total Volumes of Maternal Specimen Required

*Generally blood samples, amniotic fluid cord blood and breast milk will be tested for trend in immune profiles and coinfections.

Stool samples will be tested for intestinal parasites * Urine

urinalysis

Procedure	Specimen	1	2	3	4	5	6	7	8	9	10	11

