/Test	Required	Volume/gra	labour	7-10 Day	6 wks	10 wks	14 wks	24 wks	36 wks	48 wks	72 wks	96 wks
	(volume)	m		рр	рр	рр	рр	рр	рр	рр	рр	рр
CMV / HBV/ HCV	serum(1 mL)	✓ (1
HIV testing/all negatives	Plasma (1 mL)	1	~	1	1	1	1	1	~	1	1	1
STI serology												
Parasites At least 3 specimens	Stool(10 g) Anal swab	1	1	1	1	1	1	1	1	1	1	1
FBC/Differentials/pla telets	Plasma (5mL)	√			1		1			1		1
Markers of immune	Blood (10mL)	1		✓	✓	✓	1	1	1	1	1	√
activation, cytokines levels and trends	Cord blood (10mL)		~									
	Amniotic fluid (10mL)		1									
	Breast milk(10 mL)			1	1	1	1	1	1	1	1	1
Urine	urinalysis	1			1			1				1
Biochemistry	Plasma (5 mL)	✓			1		1			1		1
Panel	Sugar (3 mL)	√			✓		1			1		✓
Restriction factors	Cord blood		✓									
	Breast milk			1	✓	✓	✓	1	✓	1	✓	✓
				FOR	HIV POSI	TIVES ONL	Y					
T cell profile	PBMCs	✓						1	✓	 ✓ 	1	 ✓
HIV RNA load*	Whole blood	√ *										
HLA/KIR host genetics												
HIV genetic diversity for Transmission linkages**	Whole blood	~										V

Table 2: Type, Volume, intervals of collection and Purpose of Maternal Specimens Required

*Re-testing with be done for all Unsuppressed HIV load every 3 months ** for all acute HIV infections

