4.10.8 HIV Diagnosis

Qualitative rapid immunochromatographic assays, SD Bioline HIV-1/2 3.0 (Standard Diagnostics Inc., Kyonggi-do, South Korea) and Abbott'sDetermine[®]HIV-1/2will be used to detect HIV-1/-2

antibodies in mothers venipuncture whole blood specimens. Western blot test will be used as a tie breaker for any indeterminate test results.

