4.10.17 Transmission linkages

Mothers who seroconvert after enrolments will have host/viral genetics factors determined transmission linkages assessment. Peripheral blood mononuclear cells will be collected for these HUU, HEI and HEU infants for NK cell phenotype and functional analysis.

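### The readable sampling plan does not support the viral set points and acute-phase biomarkers of objective C2: acute has no time definition and means in effect any seroconversion found by antibody tests 1.4 to 24 weeks apart

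*Protocol*

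**What the plan says.** Section 3.1, under objectives for acute HIV infections, lists as C2 "To determine the viral set points, HIV suppression trends and biomarkers of immune activation". The same label defines column b of Table 5 (section 4.10.18), triggers an additional cytokine panel in section 4.10.7.2, and appears in the research outcomes of section 4.10.24 as HIV incidence and postpartum vertical transmission.

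No section says how recent an infection must be to count as acute. The nearest thing to an operational rule is in section 4.10.17: "Mothers who seroconvert after enrolments will have host/viral genetics factors determined".

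Detection is fixed in two places.
- **Schedule.** Section 4.8 has mothers enrolled in pregnancy and seen at "delivery, 10 days and 6, 10, 14, 24, 36, 48, 72 and 96 weeks postpartum thus totaling 11 visits". Table 2 carries a row for "HIV testing/all negatives", ticked at every visit.
- **Assay.** Section 4.10.8 names "Qualitative rapid immunochromatographic assays, SD Bioline HIV-1/2 3.0" and a second rapid test, used to detect "antibodies in mothers venipuncture whole blood specimens", with Western blot as tie breaker. HIV RNA appears in Table 2 only under the block for HIV-positive mothers.

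Sections 4.1 and 4.10.12 and the Table 2 footnote make repeat viral loads conditional: unsuppressed values, at or above 1000 copies/mL, are re-run after 3 months.

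Objective B1 reads "To determine vertical transmission rates of mothers with acute and chronic HIV infection on option B" (the quote stops just before the plus sign).

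**The concern.** The stated scientific interest depends on the phase of infection. Section 1.2.1 argues that biomarkers of acute infection may help predict variation in viral set point. If a woman infected days before her first positive test and a woman infected about 24 weeks before hers both enter the acute stratum, the section 4.10.7.2 markers describe a mixture of phases. The postpartum transmission outcome in section 4.10.24 would carry a phase label that the data cannot support.

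The set point raises a second problem. The protocol does not define the term. I take its usual meaning, the level at which viral load settles in untreated infection. That needs untreated viral loads at a known time since infection. The readable text gives no serial viral load schedule for seroconverters before treatment and no date for starting treatment after diagnosis. Later values may reflect treatment.

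**Working it through.** **Inputs.** Visit times come from section 4.8. There are 600 HIV-negative mothers (section 4.1). Section 4.10.18 gives 3% incidence without a time unit, and losses of 15% and 20% in years 1 and 2. Assumptions: constant hazard, full attendance at scheduled visits, and a test that turns positive once antibody is detectable.

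**Visit count.** Enrolment, delivery, 10 days and eight later visits make 11, as the protocol states.

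**Postpartum gaps L (weeks).** 1.43, 4.57, 4, 4, 10, 12, 12, 24, 24; sum 96.

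- Share of time in the two 24-week gaps: 48/96 = 50%.
- Share in gaps of 10 weeks or more: 82/96 = 85%.
- Mean delay from antibody detectability to next test: ΣL²/(2 × 96) = 1594.9/192 = 8.3 weeks; within a 24-week gap it is 12 weeks.

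**Share found within x weeks of antibody detectability** = Σmin(L, x)/96. The other rows weight each gap by retention and then add an assumed 8-week antenatal gap (enrolment at 32 weeks, delivery at 40).

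| | 4 wk | 6 wk | 8 wk | 12 wk | 50% reached at |
|---|---|---|---|---|---|
| Postpartum, no losses | 33.4/96 = 35% | 44/96 = 46% | 54/96 = 56% | 72/96 = 75% | 6.8 wk |
| With 15%/20% losses | 37% | 48% | 59% | 77% | 6.3 wk |
| Losses plus antenatal gap | 38% | 51% | 63% | 79% | 5.9 wk |

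In the first row, 50% is reached where 14 + 5x = 48, so x = 6.8. The period between infection and detectable antibody adds to each delay. Missed visits lengthen it too: one missed week-72 visit makes the interval 48 weeks.

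**Expected seroconverters.**
- No losses, 3 per 100 person-years: 600 × 96/52.18 × 0.03 = 33.
- Losses spread evenly within each 48-week half: mean retention is 0.925, then 0.85 × 0.90 = 0.765. Follow-up per woman is 48 × 0.925 + 48 × 0.765 = 81.1 weeks. Then 600 × 81.1/52.18 = 933 person-years, × 0.03 = 28.
- If 3% is cumulative: 600 × 0.03 = 18.

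Found within 4 weeks: 28 × 0.37 = 10, or 18 × 0.37 = 7.

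**Test intervals of 6 weeks or less.** Only the first four gaps qualify: 14/96 = 15% of postpartum follow-up. That gives 600 × 14/52.18 × 0.03 = 4.8, about 5 women before losses, or 18 × 0.146 = 2.6 if 3% is cumulative.

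**Sample availability.** Table 1 lists no maternal blood at visit 3 (7–10 days), while Table 2 ticks HIV testing there. Without that test the mean delay is 1608/192 = 8.4 weeks and the 4-week share is 32/96 = 33%, so the conclusion does not turn on it.

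**The case against.** The strongest reply is that acute is shorthand for infected after enrolment, set against chronic in Table 5, and that testing is close together when it is easiest to do. Up to week 14 the postpartum gaps are at most 4.6 weeks. Acute infection and set points are also absent from the summary's primary objectives, the research questions and the main hypotheses. Analysis by time since infection could sit in a statistical analysis plan that is not shown. All of this is fair and limits the weight of the point. But the case definition, the assay and the sampling schedule are protocol content, and C2 and section 4.10.7.2 use the label as a biological phase.

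A reader might also infer more than the documents support:
- **That the antibody tests are done in women on option B+.** They are not. The women retested are HIV-negative, so treatment matters only after diagnosis. B1 sits under the chronic-infection heading, and its option B+ phrase may qualify chronic infection only.
- **That most cases will not be acute.** This holds for cut-offs below about 6 to 7 weeks after antibody detectability and fails at 8 to 12. The protocol gives no cut-off.
- **That a set point cannot be observed.** This is too absolute. A woman detected late but before treatment could supply a viral load near her set point, and stored samples could be tested.
- **That viral load is scheduled at visit 1 only.** The ticks in Table 2 may have been damaged in reading. Figure 1 is not shown, and its key marks an item for acute infections only. I rely on the conditional retesting rule in the text.
- **That all of objective C fails.** C1 (incidence) can be estimated from seroconversion between visits, and C3 (genetic diversity, linkages) does not need acute-phase samples.

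**Conclusion.** The point holds for objective C2, the acute-case biomarkers of section 4.10.7.2 and the acute-transmission outcome of section 4.10.24. Followed as written, women whose antibodies became detectable anywhere from days to about 24 weeks before the first positive test are analysed as one acute group. About a third are found within 4 weeks and just under half within 6 (about half with the antenatal gap). The group is small: about 28 women, or 18 if 3% is cumulative. A set point is not identifiable from the planned sampling, because no serial untreated viral load is stated and the start of treatment is not given.

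The percentages rest on a constant hazard and full attendance. The counts also rest on reading 3% as an annual or a cumulative figure. The 24-week maximum interval and the missing time definition come directly from the document.

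**What to change.** 1. In C2, section 4.10.7.2, Table 5 column b and the acute-transmission outcome in section 4.10.24, call the group incident (recent) infection. Reserve acute for RNA-positive, antibody-negative cases or for a short, prespecified interval between last negative and first positive test. C1 and C3 can stay.
2. Run the viral load assay of section 4.10.12 on each seroconverter's first positive sample and, where suitable plasma is stored, on her last negative one. Analyse biomarkers by estimated time since infection.
3. Replace viral set points with the first viral load before treatment, reported with estimated time since infection and only for women who have such a sample.
4. Reconcile the passages on acute cases, option B+ and viral load retesting, and the disagreement between Tables 1 and 2 on maternal blood at visit 3. No treatment rule is proposed here.

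**Cost.** Relabelling, plus at most two viral loads per seroconverter: 2 × 18 = 36 to 2 × 33 = 66 tests with an assay already named. Section 4.10.1 provides for frozen storage but describes serum from clotted samples. Plasma storage appears in the Table 6 budget, so availability of the last negative sample must be confirmed. The main downside is that the group still called acute will be small: with a 6-week interval rule, about 5 women or fewer from the postpartum visits, plus any RNA-positive, antibody-negative cases.
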